1.1 SAP Summary Table

TRIAL FULL TITLE	SodiUm SeleniTe Administration IN Cardiac Surgery (SUSTAIN CSX®-trial). A multicenter, randomized controlled trial of high dose sodium-selenite administration in high risk cardiac surgical patients
TRIAL REGISTRATION	https://clinicaltrials.gov/ct2/show/NCT02002247
PROTOCOL PUBLICATION	NONE
CURRENT PROTOCOL DATE	2018-08-01
TRIAL PRINCIPAL INVESTIGATOR	[name]
TRIAL SENIOR STATISTICIAN	[name]
TRIAL COORDINATOR	[name]
STATISTICIAN(S) PERFORMING ANALYSIS	[name] and [name]
SAP AUTHOR(s)	[name], [name] and [name]
SAP DATE	2021-05-27
SAP STATUS	Version 1.- Finalized and approved.
SAP REVISION HISTORY	None yet
STATUS OF TRIAL AT TIME OF SAP FINALIZATION OF V1.0	Enrollment completed. Blinded data cleaning completed. No by arm outcome results generated yet.

1.3 Purpose, usage, and target audience of this document

This document provides a detail description of the analysis plan for the SUSTAIN CSX trial. This document is meant to be used in conjunction with the study protocol. This document does not subsume the protocol, but several elements of the protocol, such as the sample size justification are reproduced herein for completeness. This document has the following purposes:

1. Provides a written agreement between the principle investigator, sponsor, lead study statistician and data analysts regarding exactly what analysis will be performed.
2. Provides a record of the analysis plan specified prior to examining any outcomes by arm.
3. Provide clear specifications for the analyst(s) performing the data filtering/transformation, variable derivations, statistical analyses and report generation.

This document follows the guidance published in JAMA by Gamble et al (2017) and referenced at <https://www.equator-network.org/reporting-guidelines/guidelines-for-the-content-of-statistical-analysis-plans-in-clinical-trials/>¹ The SAP checklist is completed in Appendix A.

3.1 Background and Rationale

Copied from <https://clinicaltrials.gov/ct2/show/NCT02002247>

Over a million patients undergo open heart surgery annually and this number is likely to accelerate as the population ages and the prevalence of diabetes and cardiovascular disease continue to increase. Unfortunately, death, organ failure, and other serious complications are all too frequent following open heart surgery, especially in some high-risk patient populations.

Selenium is a trace element that is important for many of the body's regulatory and metabolic functions especially during times of stress. International members of the study team have shown in a non-randomized study that high dose selenium supplementation was associated with improved clinical outcomes compared to a historical control group. The next step in this program of research is to conduct a randomized trial.

3.2 Overall Aim

The aim of this trial is to investigate the effects of perioperative high dose selenium supplementation in high-risk cardiac surgical patients undergoing complicated open heart surgery. If the hypothesis is proven true, and this simple, inexpensive nutrient reduces complications and improves recovery of patients undergoing cardiac surgery, there is the potential to dramatically change clinical practice and improve health outcomes.

3.3 Study Hypotheses

Perioperative high dose selenium supplementation in high-risk cardiac surgical patients undergoing complicated open heart surgery will lead to better outcomes including lower mortality and fewer days requiring life sustaining therapies.

4 Study Methods

4.1 Trial Design

A randomized, placebo-controlled, double-blind, multicentre definitive trial of 1400 patients across 20 sites in Germany and Canada, which will include the pilot study patients. An industry partner (Biosyn) will provide the product and some additional support for the European sites. Patients will be randomized to receive either a daily perioperative high-dose selenium or placebo until postoperative day 10 (maximum) or upon earlier discharge from ICU.

4.2 Randomization

Randomization description copied from published protocol.

At each participating center the local coordinating investigator will screen daily all cardiac surgical patients scheduled to undergo cardiac surgery in the near future or on the next day. A screening

log will be kept at each site to determine the number of patients meeting the inclusion criteria, those truly eligible patients, those who consent and are randomized and reasons why potentially eligible patients did not get enrolled. Following a full explanation of the nature and purpose of the study, a written informed consent will be obtained from the patients participating in the study. At the time of enrolment into the study, patients will be randomized to receive either selenium or a matching placebo similar in appearance, consistency, volume, and smell so as to blind patients, investigators and health care practitioners as to the nature of the study medication. Patients will be consecutively randomized by a web-based randomization system (concealed and blinded) developed by the Clinical Evaluation Research Unit at the Kingston Health Sciences Centre and randomization will be stratified according to centre. Randomization will be based on the method of permuted blocks of undisclosed random size stratified by centre.

4.3 Sample Size Considerations

Sample size copied from published protocol.

The distribution of the control arm was calculated based on a database of patients that underwent cardiac surgery during a 12 month follow up at Aachen University ($n = 1127$) and would meet the inclusion criteria of the current study ($n = 170$). In our dataset, the mean (SD) POD free days was 23.2 (9.2); 4% of the patients died, 6% survived on life-sustaining therapy with 0 POD free days. We checked these numbers with data from the University of Ottawa Heart Institute (Canada), and numbers are consistent with the 4% 30-day mortality rate and the 6% not yet free from life-sustaining therapy by 30 days. We used simulation to estimate the power of applying the Wilcoxon rank-sum test to our primary outcome of PODs free days. The intervention arm was then generated by multiplying the control arm daily rate of liberation from life sustaining therapies by a fixed factor (hazard ratio) but assuming the same 4% mortality rate. The mean days on life-sustaining therapy was then subtracted from 30 to obtain the free days. 10,000 samples were simulated so the power estimate has more than a 95% chance of being accurate to within 1%. Based on the simulation, we would require 700 patients per arm to achieve 90% power at a two-sided $\alpha=0.05$ if the intervention caused as 20% relative increase in the daily rate of liberation from life-sustaining therapy but no change in mortality compared to the control arm. Based on our Aachen data, such an effect size would result in an earlier liberation of life-sustaining therapies and mean increase of 1.5 POD free days (from 23.2 to 24.7 days). We believe such an effect size is plausible and is in line with minimally clinically important differences accepted in other recent major trials in the ICU setting.²

4.4 Framework

This is a confirmatory (i.e. hypothesis testing) superiority RCT comparing the efficacy and safety of perioperative high dose selenium supplementation to placebo in high-risk cardiac surgical patients undergoing complicated open heart surgery.

4.5 Interim Analysis

None

4.6 Timing of Final Analysis

All outcomes will be analyzed once all data is collected and cleaned and after finalization of the analysis plan.

4.7 Timing of outcome assessments

Most outcome assessments were measured in hospital up to 30 days or at 6 months. The timing of each outcome is described with the outcome in section 6.1.

5 Statistical Principals

5.1 Confidence intervals and P-values

95% confidence will be presented for selected key outcomes. P-values will be two-sided without adjustment for multiplicity. However, interpretation of secondary outcomes will consider the multiplicity of tests. There is one pre-specified primary test of efficacy. $P < 0.05$ will be considered statistically significant.

5.2 Analysis populations

The primary analysis will be a modified intention-to-treat including all patients to the arm they were randomized regardless of study compliance except we will exclude randomized patients who became ineligible due to not undergoing the planned surgery AND did not receive any study medication. In addition, for key efficacy outcomes, we plan a per-protocol analysis that further excludes patients who stayed less than 24 hours in the ICU or experienced an IP-related protocol violation.

5.3 Eligibility Criteria:

Published at <https://clinicaltrials.gov/ct2/show/NCT02002247#eligibility>.

5.4 Screening, recruitment, patient flow/follow-up

A CONSORT style flow diagram will present the numbers of patients screened and all reasons excluded prior to randomization. The table will also include the number randomized to each arm and the number used in the primary analysis in each arm with reasons for the exclusion of randomized patients.

5.5 Baseline Characteristics

Baseline characteristics will be described by arm and overall using descriptive statistics only. Categorical variables will be described as counts (%). Continuous variables will be described as mean \pm SD (min to

max) and/or median [Q1 to Q3]. Separate tables will be generated for pre-operative, intra-operative, and post-operative characteristics.

The following baseline patient characteristics will be described: Age, sex, ethnicity, height, weight, BMI, Unplanned weight loss in the last 3 months, Food intake in the week prior to ICU admission, Baseline SOFA, Charlson Comorbidity Index, Functional Comorbidity Index, Patients without angina however had CCS data entered, CCS Grading(among patients with angina), NYHA Classification, EuroSCORE II classification, Manuscript classification, Duration of the surgical procedure (hours), Duration of cardiopulmonary bypass (hours), Duration of aortic clamping (hours), Baseline SF-36 (all 8 domains and 2 summary scales), Baseline Barthel ADL index, Baseline Frailty Scale, Euroscore II (%), Euroscore II (%), time from hospital admission to randomization and additional variables as explicated in the analytic dictionary.

6 Analysis

6.1 Outcome Definitions

6.1.1 Primary Outcome:

Number of days alive and free of life sustaining therapy (i.e. PODS free) in the first 30 days after the day of surgery. PFDs do not include day of surgery or days prior to surgery. Randomization is always prior to surgery and usually occurs on day of surgery, but for some patients randomization occurred prior to the day of surgery. Life sustaining therapy includes any use of the following for any duration of time on the given day: mechanical ventilation, vasopressor therapy, mechanical circulatory support, continuous renal replacement therapy, or intermittent hemodialysis. Patients who die in the first 30 days after day of surgery will be assigned 0 PODS free days.

- (1) **Mechanical ventilation:** Mechanical ventilation via an endotracheal tube or tracheostomy tube OR use of non-invasive mechanical ventilation (CPAP or BiPAP) will count as mechanical ventilation unless the patient routinely uses these modalities at home. A patient will be considered liberated from mechanical ventilation at the time of extubation if they remain off mechanical ventilation at least 48 hours. However, if patients are re-intubated within 48 hours, then the intervening time will not be considered free days.
- (2) **Vasopressor therapy:** days with more than 2 hours of any dose of norepinephrine, epinephrine, vasopressin, Dobutamine, Milrinone or Levosimendan and >5 ug/kg/min of dopamine, or > 50 ug/minute of phenylephrine, will not be considered free days. The 48-hour rule does not apply to vasopressor therapy or renal replacement therapy.
- (3) **Mechanical circulatory support:** Use of Intra-Aortic Balloon Pump (IABP) or Extra Membrane Oxygenation (ECMO) or any Left Ventricular Assist Device (LVAD, like Impella or TandemHeart, etc.) for any duration will be considered to receive Mechanical Circulatory Support on that calendar day. As with mechanical ventilation, days will not be considered free if mechanically circulatory support is re-initiated within 48 hours, but days free in the first 48 hours will count if mechanical circulatory support is re-initiated on or after 48 hours.

- (4) **Renal replacement therapy:** if the calendar day is on or between the start and stop date of any renal replacement therapy then the day is not a free day.

6.1.2 Secondary Outcomes:

1. 30-Day Mortality [Time Frame: 30 days]

Count and percentage of patients who died within 30 days from surgery.

2. Hospital Acquired Infections [Time Frame: hospitalization]

Count and percentage of patients with definite or probable infections will be reported. To be evaluated up to hospital discharge.

3. Perioperative hemodynamic profile [Time Frame: post anesthetic induction, upon ICU admission and at change of nursing shift on the morning of the first postoperative day and subsequent days in the ICU]

This includes: Heart Rate, systemic and pulmonary blood pressures, central venous pressure, cardiac output, and mixed venous blood oxygen saturation level (SvO₂).

4. Cardiovascular Complications [Time Frame: hospitalization]

This includes: clinically significant atrial fibrillation (>1 hour), myocardial injury ≥72 hours after surgery, stroke after surgery, cardiac arrest. To be assessed up to hospital discharge.

5. Duration of Mechanical Ventilation [Time Frame: hospitalization]

Duration of mechanical ventilation will be calculated from time of admission to ICU until time of discontinuation. All times of endotracheal extubation and any subsequent re-intubation/re-extubations or tracheostomy will be recorded. A patient will be considered liberated from mechanical ventilation at the time of liberation if they subsequently remain off mechanical ventilation for at least 48 hours i.e. for a patient who is removed from mechanical ventilation and reintubated 30 hours later, the intervening days from extubation to re-intubation will be considered to represent ongoing need for life support. Use of non-invasive mechanical ventilation (CPAP or BiPAP) will count as mechanical ventilation unless the patient routinely uses these modalities at home.

To be assessed up to hospital discharge.

6. Incidence of post-operative delirium [Time Frame: hospitalization]

CAM-ICU score was assessed upon admission to ICU post-operatively (not pre-operatively, may be same day as surgery or the next day) and will be reported daily while in ICU.

The CAM (Confusion Assessment Method for the Intensive Care Unit) has four features. Delirium is diagnosed when both Feature 1 and 2 are positive, along with either Feature 3 or Feature 4

Feature 1. Acute Onset of Mental Status Changes or Fluctuating Course.

- Is there evidence of an acute change in mental status from the baseline?
- Did the (abnormal) behavior fluctuate during the past 24 hours, that is, ten to come and go or increase and decrease in severity?

Feature 2. Inattention

- Did the patient have difficulty focusing attention?
- Is there a reduced ability to maintain and shift attention?

Feature 3. Disorganized Thinking

- Was the patient's thinking disorganized or incoherent, such as rambling or irrelevant conversation, unclear or illogical flow of ideas, or unpredictable switching from subject to subject?
- Was the patient able to follow questions and commands throughout the assessment?

Feature 4. Altered Level of Consciousness

- Any level of consciousness other than 'alert'.
- Alert-normal, spontaneous fully aware of environment and interacts appropriately.
- Vigilant-hyperalert
- Lethargic-drowsy but easily aroused, unaware of some elements in the environment, or not spontaneously interacting appropriately with the interviewer; becomes fully aware and appropriately interactive when prodded minimally
- Stupor-difficult to arouse, unaware of some or all elements in the environment, or not spontaneously interacting with the interviewer; becomes incompletely aware and inappropriately interactive when prodded strongly
- Coma – unarousable, unaware of all elements in the environment, with no spontaneous interaction or awareness of the interviewer, so that the interview is difficult or impossible event with maximal prodding

7. ICU Length of stay [Time Frame: ICU stay]

ICU length of stay is calculated from time of ICU admission to time and date of actual discharge.

To be assessed up to ICU discharge.

8. Hospital Re-admission Rates [Time Frame: 6-months]

To be assessed up to 6-months post-surgery. Count and proportion of patients who were admitted to hospital more than once.

9. Hospital Length of stay [Time Frame: hospitalization]

Hospital length of stay will be calculated from the date of index surgical procedure to time and date of discharge from hospital.

To be assessed up to hospital discharge.

10. 6-Month Survival [Time Frame: 6-months]

Kaplan-Meier curves of and hazard ratio of survival over 6 months starting with day of surgery.

11. Quality of Life [Time Frame: day 30, 3-months and 6-months]

The SF-36 physical and mental summary scales will be analyzed separately.

Barthel Index of Activities of Daily Living Total Score

Frailty Scale

12. Return to work [Time Frame: 6-months]

Assessed using a questionnaire to determine the patient's ability to return to their pre-operative working capabilities. To be assessed up to 6 months post-surgery.

13. 6-minute walking test [Time Frame: hospital discharge]

This was done in a sub-study of pre specified patients.

In the 6-minute walking distance (6MWD) was performed at hospital discharge and at 3 months. The analysis of the 6MWD is based on rank order where patient who died prior to testing are assigned the lowest rank, people who were unable due to illness or physical limitation were assigned a value of zero and people who did the test are ranked according to their distance walked. Patients not doing the test for other reasons (missed due to RC unavailable or unaware, missed due to hospital discharge, did not return to clinic, patient refused but able, or COVID-19 reasons) were excluded from the analysis. "Other" will be blindly adjudicated to determine difference from unable or otherwise missing.

6.1.3 Additional Outcomes:

1. Laboratory outcomes [Time Frame: hospital discharge]

Values above or below certain thresholds, depending on the variable will be reported as an 'ever' event, per patient, per group based on establish clinical standards.

2. Days alive post hospital discharge (DAPHD6M) [Time Frame: 182 days]

This is number of days in the first 182 days post-surgery date where patients were alive and discharged from the hospital. Patients who die within 182 days can still have >0 DAPHD6M if they were alive for some days after hospital discharge. A patient who is discharged on day X (where $X < 182$) and dies on day $X+2$ would be considered to have 1 DAPHD6M, because the date of discharge and the date of death are not counted as free days, but there is otherwise no minimum amount of survival required.

6.1.4 Remaining study variables:

The study analytic dictionary contains a complete list of study variables with information including their label, their REDCap location (or identified as derived), their valid values or allowable range, and the variables scale (binary, nominal, ordinal, continuous or special) which is used to determine how they will be analyzed. The complete stats report will contain the following sections reported mostly in tabular form:

- 1 Baseline Demographics (Pre-Procedure)
- 2 Baseline Demographics (Intra-operative)
- 3 Baseline Demographics (Immediate Post-operative)
- 4: Compliance with Study Investigational Product
- 5: Protocol Violations
- 6: SAEs
- 7: Treatment period assessment:
- 8: Standard Nutrition Practices
- 9: Events of Interest
- 10: Primary outcome
- 11: Secondary Outcomes
- 12: Additional Outcomes

6.1.5 Cost Utility Analysis:

A cost utility analysis will be performed if the results of this study show clear benefit of sodium-selenite administration compared to placebo. The cost effectiveness of sodium-selenite administration compared to placebo will be assessed in terms of the incremental cost per quality adjusted life year (QALY) gained from the perspective of health care system. Analysis will incorporate data on resource use and patients utility values up to 6 months post sodium-selenite administration given the assumption that no long term differences in outcome are expected. Resource use will be assessed by data collected at the follow up interviews. Utility values would be derived from SF-36 using the algorithm proposed by Brazier et al. QALYs will be estimated for each patient within the clinical trial using the total area under the curve method. The incremental cost and QALY will be estimated using a regression analysis approach. Uncertainty in the analysis will be addressed by estimating 95% CIs using a non-parametric bootstrapping method. Further details of the cost utility analysis, should it be indicated, will be detailed in a separate document.

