6.2.2 Secondary outcomes

Secondary binary outcomes such as cardiovascular complications, postoperative delirium, re-admissions, hospital-acquired infections and 30-day mortality will be compared between groups by a logistic mixed effects model with site included as a random effect.¹ Odds ratios with 95% confidence intervals will be reported.

Six-month mortality will be described by group using Kaplan-Meier curves. Survival will be compared by a hazard ratio with 95% confidence intervals and corresponding Wald test. Estimates will be derived from the Cox proportional hazards model with a random frailty for site. If the proportional hazards assumption is clearly and meaningfully violated, we will report a smoothed time dependent hazard ratio over time. However, the aforementioned overall Wald test will remain the primary test of statistical significance. Patients will be censored at the earliest of 183 days post randomization or last known follow-up.

Length of ICU and hospital stay will be summarized by arm using the quartiles of time to live discharge estimated from the subdistribution cumulative incidence function (CIF) where death is treated as a competing risk precluding the possibility of discharge. The between arm difference in time to live discharge will be tested using the Wald test from the Cox proportional hazards model with site as a random frailty to account for potential between site heterogeneity. Patients who die prior to discharge will be censored after the end of the follow-up period to account for the competing risk of death. This will yield virtually the same results as the Fine and Gray approach treating death as a competing risk precluding discharge, except we will have incorporated ICU as a random effect. This outcome is also known as time-to-discharge-alive (TTDA).

The SF-36, Barthel Index and frailty scale will be collected at baseline. At 30 days, 3 months and 6 months after surgery, we will repeat the Barthel Index and SF-36 and collect return to work data. The SF-36 physical and mental summary scales and the Barthel index will be treated as continuous variables and analyzed using a linear mixed effects model for longitudinal data. In order to include all patients

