with a baseline assessment regardless of follow-up, we will use constrained longitudinal data analysis where the independent dummy variable indicating treatment arm (1-treatment or 0-control) will be set so to 0 at baseline for both arms but 1 post baseline for the intervention arm.^{2,3} This model will include site as a random effect and will allow for unstructured within patient correlation as estimated by restricted maximum likelihood. The focus of these secondary analyses will be primarily descriptive as these outcomes are limited to survivors and no imputation for decedents is planned. Thus, these outcomes will not be informative of treatment efficacy if they are in the opposite direction from survival. The between group difference in the change from baseline to the various follow-up time points will be described as expected means with 95% confidence intervals.

6.2.3 Additional outcomes:

Days alive and home in 6 months will be analyzed using the same approach as PFDs.

Variables collected but not specifically listed above will be described by arm at each time they were collected using counts and percentages for categorical variables and medians and quartiles or means and standard deviations for continuous variables. Post baseline differences in these variables will be tested using the Cochran-Mantel-Haenszel test stratified by site for the categorical variables and the van Elteren test stratified by site for continuous variables. Analysis of these variables will be considered exploratory so no adjustment for multiplicity will be applied to p-values, but multiplicity of tests will be considered in when interpreting these results.

Study reporting will be in accordance with the CONSORT statement.⁴

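### Re-admission to 6 months has no rule for death, so on the natural reading a patient who dies before any re-admission counts as not re-admitted, which modestly favours the arm with more deaths

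*SAP*

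**What the plan says.** Section 6.1.2, item 8, gives the window and the measure for re-admission: "To be assessed up to 6-months post-surgery", then "Count and proportion of patients who were admitted to hospital more than once". Section 6.2.2 places it among the binary secondary outcomes, which are "compared between groups by a logistic mixed effects model with site included as a random effect" and reported as odds ratios with 95% confidence intervals.

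Section 5.2 describes the primary analysis as "modified intention-to-treat including all patients to the arm they were randomized regardless of study compliance", with one narrow exclusion for patients who had neither the planned surgery nor any study medication. No separate set is named for re-admission. Neither section limits the denominator to patients discharged alive, treats death as a competing event or forms a composite.

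For comparable outcomes the SAP does say what happens to patients who die:
- **Primary outcome (6.1.1):** death within 30 days gives zero free days.
- **ICU and hospital stay (6.2.2):** "where death is treated as a competing risk precluding the possibility of discharge".
- **6-minute walk (6.1.2, item 13):** "patient who died prior to testing are assigned the lowest rank".
- **SF-36 and Barthel Index (6.2.2):** "these outcomes are limited to survivors and no imputation for decedents is planned", with a warning that these results do not inform on efficacy if they run opposite to survival.

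Re-admission has neither a rule nor a warning.

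**The concern.** Re-admission is an unfavourable event, and death removes the chance of it. A patient who dies in the index stay, or at home without going back to hospital, was not admitted more than once. In a yes/no proportion over all analysed patients, that patient therefore counts as a good result. If the arms differ in mortality, the odds ratio moves in favour of the arm with more deaths, even when patients at risk are re-admitted equally often in both arms.

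Equal mortality cannot be taken for granted, because lower mortality under selenium is part of the hypothesis in section 3.3. If selenium does save lives, this definition makes its re-admission result look worse than it is. If it costs lives, the definition makes the result look better. The denominator is also left for the analyst to choose, although it can be fixed in one sentence.

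**Working it through.** The SAP gives no planning figure for re-admission, so there is nothing to reproduce. What follows is an illustration.

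**Inputs**
- r, the re-admission risk among patients discharged alive, the same in both arms: assumed 15% to 35%.
- m, the share who die before discharge: assumed 2% in one arm and 5% in the other.
- 700 patients per arm: SAP section 4.3.

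**Formulae**
- Proportion re-admitted among all patients: p = r × (1 − m).
- Odds ratio (more deaths versus fewer): [p₂/(1 − p₂)] / [p₁/(1 − p₁)].
- Re-admitted or dead: c = m + r × (1 − m).

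**Results, 2% versus 5% deaths**

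| r | p, fewer deaths | p, more deaths | Gap (points) | OR, re-admission | c, fewer versus more deaths | OR, composite |
|---|---|---|---|---|---|---|
| 15% | 0.15 × 0.98 = 14.70% | 0.15 × 0.95 = 14.25% | 0.45 | 0.96 | 16.70% vs 19.25% | 1.19 |
| 25% | 0.25 × 0.98 = 24.50% | 0.25 × 0.95 = 23.75% | 0.75 | 0.96 | 26.50% vs 28.75% | 1.12 |
| 35% | 0.35 × 0.98 = 34.30% | 0.35 × 0.95 = 33.25% | 1.05 | 0.95 | 36.30% vs 38.25% | 1.09 |

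The re-admission odds ratio favours the arm with more deaths in every row. The composite goes the other way in every row.

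**Size against sampling error.** At r = 25%, the standard error of the difference is √(0.245 × 0.755/700 + 0.2375 × 0.7625/700) = 2.29 points. The gap of 0.75 points is 0.33 of a standard error. A two-sided 5% normal test would then reject about 6.2% of the time. Over the range of r the figure runs from about 5.7% to 7.0%.

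**Starting from the SAP's 4% planning mortality.** Section 4.3 uses 4% at 30 days in both arms. Taking 4% as m in one arm and an assumed value in the other, with r at 20%, 30% and 40% (assumed):

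| Deaths first | OR at r = 20%, 30%, 40% | Rejection rate of a 5% test |
|---|---|---|
| 4% vs 4% | 1.00, 1.00, 1.00 | 5.0% |
| 4% vs 6% | 0.974, 0.971, 0.967 | 5.4% to 6.1% |
| 4% vs 8% | 0.949, 0.942, 0.934 | 6.7% to 9.5% |
| 4% vs 12% | 0.899, 0.887, 0.871 | 12.1% to 23.7% |

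At 4% versus 8%, the composite odds ratios are 1.19, 1.13 and 1.10.

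**The case against.** **The denominator is inferred.** Item 8 says only patients, and section 6.1.4 sends variable-level detail to an analytic dictionary that is not shown. This is fair, and it is why the point rests on the natural reading and not on an express rule. It does not remove the gap, since the treatment of death belongs with the outcome definition and the SAP states it there for other outcomes.

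**The effect is small and mortality is visible.** Section 4.3 plans for equal mortality, under which there is no bias. The SAP also reports 30-day mortality, 6-month survival and days alive after hospital discharge, so a large imbalance would be seen. Re-admission is one of 13 listed secondary outcomes and section 5.1 names a single primary test. All of this stands, and it limits the weight of the point. It does not make the odds ratio right when mortality differs.

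**The all-patient proportion is a legitimate quantity.** It describes the re-admission burden that actually occurred. This stands too, and is a reason to keep it as a description. It does not support a claim that one arm does better.

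**The length-of-stay method is no remedy.** A reader might expect that approach to carry over. It keeps patients who die at risk past the end of follow-up as never having the event. That penalises death when the event is discharge, but rewards it when the event is re-admission. Cumulative incidence with death as a competing event does not help either: with complete follow-up it equals the simple proportion. Restricting to patients discharged alive conditions on a post-randomisation event and leaves deaths at home untouched.

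**A stronger reading that the SAP does not support.** A reader might infer that patients lost to follow-up are also counted as not re-admitted, so that the rate is understated. No text says so. Section 6.3 has missing items presented by arm for each outcome, which points to a missing category.

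**Conclusion.** The point holds as a modest one. The SAP makes re-admission a yes/no proportion with a logistic odds ratio and no rule for death. On the natural modified intention-to-treat reading, patients who die before any re-admission then score as not re-admitted. The direction is certain whenever mortality differs: the arm with more deaths gains. The size rests on assumed rates. It is an odds ratio of about 0.95 to 0.96 at 2% versus 5% deaths before discharge and 15% to 35% re-admission, and exactly 1 if mortality is equal. Only a mortality gap such as 4% versus 12% would distort the test seriously. The primary conclusion of the trial is not affected.

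**What to change.** 1. Add to section 6.1.2, item 8, and section 6.2.2 the outcome re-admitted or dead by 6 months, in all modified intention-to-treat patients. Compare it with the same logistic mixed model with site as a random effect. State that any between-arm conclusion about re-admission rests on this analysis.
2. Keep the re-admission proportion as a description with its denominator stated, shown beside mortality. Attach the caveat that section 6.2.2 already gives for SF-36 and Barthel: it does not inform on efficacy if it runs opposite to survival.
3. If re-admission dates are held, a cause-specific hazard model for first re-admission after live discharge may be added as supportive, censoring at death or last contact. State that it conditions on a post-randomisation event, and do not carry deaths past the end of follow-up as in the length-of-stay analysis.

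The first two changes use re-admission and survival data that the SAP already plans to analyse. Section 1.1 records that no by-arm results existed when the SAP was finalised, so the change could have been made then without knowledge of the results. The cost is some wording and one extra analysis. The downside is a composite that mixes events of different severity, so its two components should be shown alongside it.
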